1. LIST OF ABBREVIATIONS AND ACRONYMS

A list of abbreviations used in the SAP.

Term/Abbreviation	Definition
HCQ	hydroxychloroquine
PEP	post-exposure prophylaxis
SARS-CoV-2	severe acute respiratory syndrome coronavirus 2

2. INTRODUCTION

This is a randomized, multi-center, placebo-equivalent (ascorbic acid) controlled, blinded study of the efficacy of hydroxychloroquine (HCQ) post-exposure prophylaxis (PEP) for the prevention of severe acute respiratory syndrome coronavirus 2 (SARS-CoV-2) infection in adults exposed to the virus.

2.1. GENERAL DESIGN CONSIDERATIONS

Evaluations include safety and tolerability, SARS-CoV-2 detection, SARS-CoV-2 viral shedding, and coronavirus disease (COVID-19) diagnosis. Two study groups (one active and one receiving ascorbic acid [vitamin C], to serve as a placebo-equivalent comparator) will be enrolled to assess a daily dosing regimen administered for 14 days, which appears to be the upper limit of the incubation period of SARS-CoV-2 infection.

Up to 2000 eligible participants 18 to 80 years of age will be randomized (at the level of household) 1:1 to receive one of the following therapies:

- HCQ 400 mg orally daily for 3 days then 200 mg orally daily for an additional 11 days
- Ascorbic acid 500 mg orally daily for 3 days then 250 mg orally daily for 11 days

HCQ and ascorbic acid will appear similar, and taste will be partially masked as HCQ can be bitter and ascorbic acid will be sour.

During the study participants will perform the following:

- Collect mid-nasal swabs for viral detection for the primary trial endpoint
- Complete Surveys that will include questions about symptoms from both the drug regimen and virus infection, review of concomitant medications, and other pertinent topics

Note: Participants who report respiratory or other febrile illness will be referred for assessment to their primary care provider.

During the first 14 study days, participants take medication, complete Surveys, and collect mid-nasal swab to assess symptoms and virus exposure. On Day 28, a final swab is collected and Survey completed. The duration of study participation will be approximately 28 days.

2.2. STUDY OBJECTIVES AND ENDPOINTS

This document focuses on the statistical procedures for the primary and secondary objectives and endpoints listed in the following table.

Objectives	Endpoints
Primary	
To test the efficacy of HCQ (400 mg orally daily for 3 days then 200 mg orally daily for an additional 11 days, to complete 14 days) to prevent incident SARS-CoV-2 infection, compared to ascorbic acid among contacts of persons with SARS-CoV-2 infection	Polymerase chain reaction (PCR)-confirmed SARS-CoV-2 infection through Day 14
Secondary	
To determine the safety and tolerability of HCQ as SARS-CoV-2 PEP in adults	Adverse events
To test the efficacy of HCQ (400 mg orally daily for 3 days then 200 mg orally daily for an additional 11 days, to complete 14 days) to prevent incident SARS-CoV-2 infection two weeks after completing therapy, compared to ascorbic acid among contacts of persons with SARS-CoV-2 infection	Polymerase chain reaction (PCR)-confirmed SARS-CoV-2 infection through Day 28
To test the efficacy of HCQ to shorten the duration of SARS-CoV-2 shedding among those with SARS-CoV-2 infection in the HCQ PEP group	SARS-CoV-2 viral shedding by PCR
To test the efficacy of HCQ to prevent incident COVID-19	PCR-confirmed COVID-19 diagnosis post start of HCQ therapy

2.3. RANDOMIZATION

Enrolled contacts were randomized 1:1 to receive either HCQ or ascorbic acid. Randomization tables were stratified by study site and contact type (household/social exposure or healthcare worker exposure) and blocked into groups of randomly varying size. The tables were programmed in R and allocation was performed via REDCap by site pharmacists or their designees. All other study staff were blinded to randomization group apart from the coordinating center's unblinded statistical team.

2.4. SAMPLE SIZE AND POWER

Since finalization of the protocol and at the recommendation of the DSMB, the study size has been recalculated as an event-driven design. The original study was designed under 80% power with a target number of households, assuming 1 infection per household, recognizing there would

likely be more than 1 per household and therefore power would be at least 80%. In the spirit of accounting for the within household correlation without any existing estimates of what it may be, we instead assume 90% power with 50% reduction and 4 interim analyses (for 5 total) and a one-sided alpha = 0.025 and a hard futility boundary. Under these design assumptions, the design requires 93 events. Assuming a household attack rate of 10% in the placebo arm (higher than in protocol and based on emerging evidence (UM study and HH study from China that looked at masks and disinfecting), we would need to enroll 1240 participants who are negative at baseline.

3. GENERAL DATA ANALYSIS CONSIDERATIONS

3.1. ANALYSIS SET(S)

This section describes the cohorts for the primary, secondary and exploratory analyses described in this document.

Intention to Treat (ITT) Cohort: The ITT Cohort includes all contacts enrolled into the study.

Modified Intention to Treat (mITT) Cohort: Contacts who are SARS-CoV-2 negative by PCR at the baseline visit.

mITT Sensitivity Cohort: Contacts in the mITT cohort who are SARS-CoV-2 negative by PCR at the day 1-3 visits. Participants who are SARS-CoV-2 negative on two of the three days, without a SARS-CoV-2 positive result, will be included in this cohort.

Seronegative Cohort: If a validated, sensitive and specific assay is available for antibody testing, this cohort will include all mITT cohort participants who are antibody negative at baseline.

Infected Cohort: Contacts who are SARS-CoV-2 positive by PCR at the baseline visit.

PK Cohort: Participants from the DBS Sub-study with at least 1 interpretable PK sample

Household Cohort: All enrolled index cases and their household contacts. Enrolled indexes are enrolled in either the PEP Study or the companion Early Treatment Study.

Index Cohort: All enrolled index cases.

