The duration of study participation will be approximately 28 days. Households will be randomized 1:1 (at the level of household), with close contact participants receiving one of the following therapies:

- HCQ 400 mg orally daily for 3 days then 200 mg orally daily for an additional 11 days
- Ascorbic acid 500 mg orally daily for 3 days then 250 mg orally daily for 11 days

After 14 days of treatment are completed, participants will be asked to participate in the study for an additional 14 (± 3) days.

Eligible index cases will be asked to provide a mid-nasal swab at baseline to determine the viral load and complete a questionnaire at baseline and on Day 28 to report their clinical course.

2. Schedule of Activities

Procedure	Screening	Self-Quarantine							Exit Contact ^b
		Treatment Period							
	Day 0 ^a	Day 1 ^a	Day 2	Day 3	Days 4 to 7	Day 8	Days 9 to 13	Day 14	Day 28 (±3 days)
Informed consent	X	X ^c							
Demography	X	X ^c							
Past and current medical conditions, including known pregnancy and/or lactation status	X								
Concomitant medications	X								
Exposure to index case information	X								
Inclusion and exclusion criteria	X	X ^c							
Randomization	X								
Mid-nasal swab		X	X	X	X	X	X	X	X
Study therapy (HCQ or ascorbic acid)		##	##	##	#	#	#	#	
Daily Survey (including dosing and swab adherence, concomitant medications, and symptoms review)		X	X	X	X	X	X	X	
Exit Contact Survey (including concomitant medications, symptoms, etc.)									X
Adverse Event review		X	X	X	X	X	X	X	X
If in sub-study: dried blood spot sample for HCQ concentration and anti-SARS-CoV-2 antibodies (if possible)		X	1 to 5 samples (no more than 1 per day) after dosing start						X
Index case participant mid-nasal swab		X							
Index case participant questionnaire		X							X

EOS: end of study; HCQ: hydroxychloroquine; HIPAA: Health Insurance Portability and Accountability Act; SARS-CoV-2: severe acute respiratory syndrome coronavirus 2.

Note: ## denotes either 400 mg dose HCQ or 500 mg dose of ascorbic acid (depending on group assignment); # denotes either 200 mg dose HCQ or 250 mg dose of ascorbic acid (depending on group assignment).

^a Screening and Day 1 evaluations will be conducted through a web-based screening tool, HIPAA-compliant video conference (Telehealth), telephone, or text messaging. Screening and Day 1 evaluations may occur on the same day.

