6.1. Close Contact Participants

6.1.1. Inclusion Criteria

Participants are eligible to be included in the study only if all of the following criteria apply:

1. Men or women 18 to 80 years of age inclusive, at the time of signing the informed consent
2. Willing and able to provide informed consent
3. Had a close contact of a person (index) with known PCR-confirmed SARS-CoV-2 infection or index who is currently being assessed for COVID-19

Close contact is defined as:

- a. Household contact (i.e., residing with the index case in the 14 days prior to index diagnosis or prolonged exposure within a residence/vehicle/enclosed space without maintaining social distance)
 - b. Medical staff, first responders, or other care persons who cared for the index case without personal protection (mask and gloves)
4. Less than 4 days since last exposure (close contact with a person with SARS-CoV-2 infection) to the index case
 5. Access to device and internet for Telehealth visits
 6. Not planning to take HCQ in addition to the study medication

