6.1.2. Exclusion Criteria

Participants are excluded from the study if any of the following criteria apply:

1. Known hypersensitivity to HCQ or other 4-aminoquinoline compounds
2. Currently hospitalized
3. Symptomatic with subjective fever, cough, or shortness of breath
4. Current medications exclude concomitant use of HCQ
5. Concomitant use of other anti-malarial treatment or chemoprophylaxis, including chloroquine, mefloquine, artemether, or lumefantrine.
6. History of retinopathy of any etiology
7. Psoriasis
8. Porphyria
9. Known bone marrow disorders with significant neutropenia (polymorphonuclear leukocytes <1500) or thrombocytopenia (<100 K)
10. Concomitant use of digoxin, cyclosporin, cimetidine, amiodarone, or tamoxifen
11. Known moderate or severe liver disease
12. Known long QT syndrome
13. Severe renal impairment

14. Use of any investigational or non-registered drug or vaccine within 30 days preceding the first dose of the study drugs or planned use during the study period

6.2. *Index Cases*

6.2.1. *Inclusion Criteria*

1. Men or women ≥ 18 years of age inclusive, at the time of signing the informed consent
2. Willing and able to provide informed consent
3. Currently diagnosed with known PCR-confirmed SARS-CoV-2 infection or is currently being assessed for COVID-19
4. A close contact is enrolled in the study

6.2.2. *Exclusion Criteria*

1. Currently hospitalized

6.3. *Screen Failures*

Screen failures are defined as participants who consent to participate in the clinical study but are not subsequently randomly assigned to study treatment. A minimal set of screen failure information is required to ensure transparent reporting of screen failure participants to meet the Consolidated Standards of Reporting Trials publishing requirements and to respond to queries from regulatory authorities. Minimal information includes demography, screen failure details, eligibility criteria, and any serious adverse event (SAE).

Individuals who do not meet the criteria for participation in this study (screen failure) can be rescreened if there is a change in their eligibility.

6.4. *Recruitment*

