7.1.1. Primary efficacy analyses

Objective: To estimate the efficacy of HCQ (400 mg orally daily for 3 days then 200 mg orally daily for an additional 11 days, to complete 14 days) to prevent incident SARS-CoV-2 infection, compared to ascorbic acid among contacts of persons with SARS-CoV-2 infection.

Outcome: Polymerase chain reaction (PCR)-confirmed SARS-CoV-2 infection through Day 14

Cohorts: mITT Cohort, Sensitivity Cohort

Definition of Endpoint: An endpoint defining PCR test is defined as one with either concordant results or $Ct \leq 40$ and will be referred to as positive test for this analysis. PCR tests not meeting these criteria will be referred to as negative. A participant will be defined as having reached the endpoint on the midpoint between the days of collection of their first positive result and last negative result (prior to the positive result) in the first 13 days of follow-up. Participants who have confirmed COVID-19 through external evaluation in the first 13 days (e.g. hospital or clinical assessment) will be defined as having reached the endpoint at the midpoint between the last prior negative test and the day of the external diagnosis. Participants who do not reach the endpoint will have their follow-up censored at their last negative RNA test. Any uncertainty in final endpoint determination will be resolved by the blinded Endpoint Adjudication Committee.

Analysis Details:

The primary analysis will be performed on the mITT Cohort. A sensitivity analysis will be performed on the Sensitivity Cohort to account for potential missed infections at day 1.

We will use a Cox Proportional Hazards model with robust standard errors to estimate the hazard ratio and corresponding 95% confidence interval and Wald test statistic. Efficacy will be calculated as 1 minus the hazard ratio (treatment/control) from the treatment coefficient. Robust confidence intervals and p-values will be displayed. Per FDA guidance on prevention studies, the following variables will be included to increase precision: quarantine status, sex, and age of contact.

The number of evaluable participants per arm will be displayed (defined as participants with at least one PCR test result or external diagnosis) by arm with person-days of follow-up and number of endpoints per arm and prevalence of endpoints (number reached endpoint/number evaluable) with a 95% confidence interval calculated using exact binomial confidence intervals.

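### No eligibility or analysis-set rule removes contacts already infected before enrolment, so residual shedding can count as an incident primary endpoint; the Seronegative Cohort that would test this is not assigned to that endpoint

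*SAP*

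**What the plan says.** **Eligibility.** Protocol 6.1.1 admits a person who "Had a close contact of a person (index) with known PCR-confirmed SARS-CoV-2 infection or index who is currently being assessed for COVID-19". Household contact includes anyone "residing with the index case in the 14 days prior to index diagnosis". Protocol 6.1.2 opens with "Participants are excluded from the study if any of the following criteria apply" and lists 14 items. None concerns an earlier positive SARS-CoV-2 test or earlier COVID-19. The nearest item is "Symptomatic with subjective fever, cough, or shortness of breath", which covers present symptoms only.

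**History.** The Schedule of Activities (Protocol section 2) collects "Past and current medical conditions, including known pregnancy and/or lactation status" at Day 0, but no eligibility or analysis rule uses earlier SARS-CoV-2 infection. The condition list in SAP section 6 has no item for it. That section has a broad category for infections other than HIV, but lists no variable under it.

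**Primary population.** The SAP 3.1 mITT is "Contacts who are SARS-CoV-2 negative by PCR at the baseline visit". Protocol 11.2 adds that the index case must be positive, but nothing about the contact's own past.

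**Primary endpoint.** Under SAP 7.1.1, the first positive test in the first 13 days of follow-up is the endpoint. A test is positive if it is concordant or has Ct of 40 or below. No second positive is required.

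**Serology.** SAP 3.1 defines a Seronegative Cohort: if a validated assay is available, "this cohort will include all mITT cohort participants who are antibody negative at baseline". SAP 7.1.1 assigns "Cohorts: mITT Cohort, Sensitivity Cohort" to the primary endpoint. The Seronegative Cohort is named only for the secondary COVID-19 diagnosis analysis in SAP 7.1.2. The subgroup list in SAP 7.1.4 includes neither serostatus nor earlier infection.

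**The concern.** The primary objective is to prevent incident infection, so the primary population should be people still at risk. A household member who was infected first and has recovered is eligible. If that person is at the tail of the infection, the Day 1 swab can be negative and a later daily swab positive. Prophylaxis started after the fact cannot prevent that positive.

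The trial is now event-driven (SAP 2.4). Each such event takes a place among the 93 without carrying information about prevention. It also moves the estimate toward no effect in a design whose futility bound is binding (SAP 8.1).

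The plan applies its own remedy where it is needed less. The COVID-19 endpoint requires symptoms as well as PCR. The primary endpoint can be met by PCR alone, so it is more exposed to residual shedding.

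**Working it through.** **1. Reproduce the design figures.** Inputs from SAP 2.4: hazard ratio 0.5, one-sided alpha 0.025, 90% power, four interim looks plus a final, control risk 10%.

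- Fixed-sample events (Schoenfeld): 4 × (1.960 + 1.282)² / (ln 0.5)² = 87.5. The plan's 93 is 93 / 87.5 = 1.063 times this, an allowance for the interim looks.
- A simulation with the SAP Table 1 efficacy and binding futility bounds at 19, 37, 56, 74 and 93 events, taking information as events/4, gives alpha 0.025 and power 90.2% at a hazard ratio of 0.5.
- Participants: 93 / ((0.10 + 0.05) / 2) = 1240.

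Both stated figures reproduce. Events are treated as independent within households, because no correlation estimate is given.

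**2. Add residual positives.** Let q be the share of the mITT previously infected and r the chance that such a contact has a later qualifying positive, equal in both arms. Previously infected contacts are assumed to have no new infection.

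- Control risk = 0.10(1 − q) + qr
- HCQ risk = 0.05(1 − q) + qr
- Hazard ratio ≈ HCQ risk / control risk (risks are low); efficacy = 1 − this ratio
- Share of events that are not incident = 2qr / (control risk + HCQ risk)

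Example, q = 5% and r = 30%: control 0.095 + 0.015 = 0.110; HCQ 0.0475 + 0.015 = 0.0625; ratio 0.568; efficacy 43.2%. Non-incident share 0.03 / 0.1725 = 17.4%, or 16 of 93 events.

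Power below comes from the same simulation at the diluted hazard ratio, still with 93 events.

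| q (assumed) | r (assumed) | Hazard ratio | Efficacy | Non-incident events of 93 | Power |
|---|---|---|---|---|---|
| 0 | – | 0.500 | 50% | 0 | 90.2% |
| 1% | 5% | 0.503 | 49.7% | 0.6 | 89.8% |
| 2% | 10% | 0.510 | 49.0% | 2.5 | 88.5% |
| 5% | 10% | 0.525 | 47.5% | 6.1 | 85.7% |
| 5% | 30% | 0.568 | 43.2% | 16 | 75.6% |
| 10% | 30% | 0.625 | 37.5% | 29 | 59.8% |

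The documents give neither q nor r, so every row but the first is a scenario.

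**3. Previously infected contacts who stay negative.** They add no events and, if balanced by arm, leave the hazard ratio essentially unchanged. With r = 0 and q = 5%, reaching 93 events takes 93 / (0.075 × 0.95) = 1305 contacts instead of 1240. The cost is enrolment, not power at 93 events.

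**4. What the existing safeguards catch.**

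- The Day 1-3 negative cohort (SAP 3.1) drops a re-positive on Day 2 or 3, but not one first seen later.
- The Ct 38 analysis (SAP 7.1.3) drops single-target positives with Ct above 38 and up to 40. Two-target positives count at any Ct.
- Blinded adjudication (SAP 7.1.1) is for endpoints in doubt. No rule tells the committee to weigh earlier infection.

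The first two are sensitivity analyses and leave the primary result as it is.

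**The case against.** The strongest reply is that the problem may be very small. Protocol 3.1 starts from the premise that the population has no acquired immunity. Protocol 5.1 reports 328 cases in King County and 158 in New York City, beside populations of 3.5 and 8.6 million: below 0.01% in each place (328 / 3,500,000 = 0.009%). The stated goal is effectiveness for public health control, for which an unscreened contact population is defensible. SAP 2.3 describes randomization in the past tense, so a new entry criterion may reach few people or none. Dried blood spots are optional and the assay is conditional (Protocol 10.4).

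Much of this stands. The low rows of the table are plausible. But the case counts are from March 2020, describe communities rather than households of cases, and rest on testing that Protocol 3.1 calls limited. They do not bound q. The no-immunity premise may explain why no criterion was written; it does not supply one. The two SAP changes do not depend on enrolment being open.

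A reader might infer that asking about confirmed earlier infection would recover the whole loss in the 38-43% efficacy rows. The documents do not support that. Those rows count everyone previously infected, while such a question finds only those with a test or diagnosis. With r = 30%, a confirmed share of 0.5% gives efficacy of 49.3%, and 1% gives 48.5%.

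**Conclusion.** The gap is real. No rule in either document separates residual shedding from new infection in the primary analysis, and the cohort that would test this is not assigned to the primary endpoint. The consequence is bias toward the null and lost power: from negligible (under 2 points of power at q of 1-2% and r of 5-10%) to material (about 43% efficacy and 76% power at q = 5% and r = 30%). This rests on assumed q and r, on residual positives being equal by arm, and on the SAP's 10% risk and 50% reduction holding in susceptible contacts.

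Two stronger readings should be resisted. A reader might infer that a false positive trial becomes more likely; with equal residual shedding and no drug effect, the hazard ratio stays at 1 and type I error is not inflated. A reader might also infer that recovered contacts who stay negative reduce power; at a fixed 93 events they do not. This is a cheap improvement to the primary analysis, not a threat to the trial's validity.

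**What to change.** 1. **SAP 7.1.1 and the Day 28 analysis in 7.1.2.** Add the Seronegative Cohort as a sensitivity analysis, using the same Cox model, run where Day 1 dried-blood-spot serology and a validated assay exist. This is the most useful change, because serology can find earlier infections that were never tested.
2. **SAP 3.1.** Exclude from the primary mITT any contact with a documented positive SARS-CoV-2 test or COVID-19 diagnosis before randomization, where the Day 0 history records it. Make the decision blind to arm. These contacts stay in the ITT and safety analyses. Align the mITT text in Protocol 11.2.
3. **Protocol 6.1.2, only if enrolment is still open.** Ask at Day 0 about an earlier positive test or diagnosis, and add it as an exclusion.

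Items 2 and 3 catch only confirmed earlier infections.

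**Cost.** One more run of an existing model, one line in SAP 3.1 and, where still possible, one screening question. No new visit or sample is needed. Slightly fewer contacts are evaluable, the Day 0 history may be incomplete because it was collected in general terms, and the seronegative analysis is limited to participants who gave a Day 1 blood spot.

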4. GENERAL ANALYSIS METHODS

Descriptive statistics that will be used to summarize continuous variables are as follows: mean and standard deviation, median and interquartile range, quartiles, range, and number of missing data values. For categorical variables, descriptive statistics that will be used include the following: frequencies, relative frequencies, and the number of missing data values. Descriptive analyses summarizing baseline and follow-up data will be stratified by site. Line, scatter and box plots will be used, as appropriate, for longitudinal data representations. A two-sided alpha level of 0.05 will be used for all statistical tests unless otherwise specified.

